## STUDY SYNOPSIS

SPONSOR / PRINCIPAL INVESTIGATOR	The Methodist Hospital Research Institute / A. [name]
TITLE:	Ciprofloxacin for Prevention of BK Infection in Renal Transplant Recipients
OBJECTIVES:	
The primary objective of this study is
 
 
• To evaluate the efficacy of routine ciprofloxacin administration post-transplantation for the reduction of the incidence of BK infection in renal transplant recipients
 
 
Secondary objectives include:
 
 
• To evaluate the safety and tolerability of routine ciprofloxacin administration in kidney transplantation
 

TRIAL DESIGN:	The proposed study is a single-center, randomized, prospective, double-blind, placebo-controlled study
TYPE AND NUMBER OF SUBJECTS:	The study will be comprised of 180 kidney transplant subjects
RANDOMIZATION	2:1 study regimen to comparator group
STUDY REGIMEN	Ciprofloxacin 500 mg (dispensed as two-250 mg capsules) once daily for up to 90 days post-transplant
COMPARATOR REGIMEN	Placebo, dispensed as two-matching capsules, once daily for up to 90 days post-transplant
Main Inclusion criteria	
 
1. Male or female subjects over the age of 18 years
 
2. Recipients of a primary or repeat renal allograft either alone (from a deceased or living donor) or as a dual-kidney transplant
 
3. Signed informed consent form prior to any research assessment
 

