## 1 Introduction

### 1.1 Background

BK virus is a member of the virus family polyomaviridae (“polyoma”). The virus, which can manifest as a viral nephritis, was first described in a renal transplant recipient in 1971, however it was not until the past decade that infection with BK virus became known as an important contributor to graft dysfunction and graft loss after renal transplantation. It has been widely accepted that emergence of BK virus correlates with the more potent immunosuppressive agents currently used to lower acute rejection rates ([1] Brennan et al. Am J Transpl 2005; 5(3):583-94). In contrast to other opportunistic infections after transplantation, for which routine prophylactic agents are administered, there is no effective agent for the prevention of BK infection, nor is there an effective agent for treating BK infection once it occurs.

Ciprofloxacin is a well known anti-infective agent in the fluoroquinolone class of antibiotics. It is most active against gram-negative enteric pathogens, and is commonly used for a variety of infectious indications.

Though classified as antibacterial agents, fluoroquinolones have been suggested to exhibit anti-BK viral effects by interfering with helicase activity of the BK virus large T antigen ([2] Ali et al. Antivir Ther 2007; 12:1-6). Ciprofloxacin has been shown in previous studies to reduce urine BK viral load ([3] Leung et al. Clin Infect Dis 2005; 40:528), and BK-associated hemorrhagic cystitis ([4] Miller et al. Biol Blood Marrow Transplant 2011) in the stem cell transplant population. Ciprofloxacin has also been associated with a lower incidence of BK viremia in one retrospective study in kidney transplant recipients ([5] Gabardi et al. Clin J Am Soc Nephrol 2010; 5: 1298). Based on these reports, we hope to find a reduction BK viremia and BK nephropathy using a prospective, randomized study design.

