### **4 Experimental Plan**

#### **4.1 Study Design**

This is a single-center, randomized, prospective, double-blind, placebo-controlled study. Eligible subjects who enroll in this study will be randomized prior to discharge from the initial transplant hospitalization in a 1:2 ratio standard of care (placebo), or 90 days of once-daily ciprofloxacin. Patients will be stratified based on the use of alemtuzumab (Campath) induction.

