#### **4.1.2 Number of Subjects**

A total of 180 kidney transplant recipients will be enrolled.

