## 5.2.4 Induction agents

Induction therapy will be determined by the prescriber based on the centers standard of care protocol.

5.2.4.1 Patients will be stratified upon enrollment based on alemtuzumab induction.

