## **7 Blinding**

### **7.1 Blinding Method**

This is a double-blind, randomized, prospective study. Subjects will be assigned to a double-blind treatment arm in the order in which they meet the criteria for randomization. The pharmacist will be unblinded to treatment. All other study site staff and all members will remain blinded to treatment arm except as described below.

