## **8 Statistical Analysis Plan**

### **8.1.1 Data Analysis**

A full analysis will be conducted based on the intent-to-treat (ITT) population. The ITT population will be defined as all randomized subjects who take at least one dose of the assigned therapy after randomization. A per-protocol analysis will be performed on all randomized patients completing 90 days of study drug. The primary endpoint of the difference in proportion of patients developing BK infection within 6 months will be determined using the chi-square test. All secondary and safety outcomes will be analyzed using chi-square or fisher exact testing for categorical variables, and analysis of variance or t-tests for continuous variables. Time to BK infection and graft survival will be estimated using Kaplan-Meier methodology. Univariate and multivariate proportional hazards Cox models will be developed to determine the risk factors of study outcomes.

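### Randomization is stratified by alemtuzumab induction, but the primary test is an unstratified chi-square, which may give up a few points of power if induction strongly predicts BK infection

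*Combined protocol and SAP*

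**What the plan says.** Section 4.1 (Study Design) sets one stratification factor: "Patients will be stratified based on the use of alemtuzumab (Campath) induction". Section 5.2.4 (Induction agents) repeats it: "Patients will be stratified upon enrollment based on alemtuzumab induction". On the mechanics of allocation, section 7.1 says only "Subjects will be assigned to a double-blind treatment arm in the order in which they meet the criteria for randomization". Section 7.2 mentions a randomization schedule but not how it is built.

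The primary analysis in section 8.1.1 is "The primary endpoint of the difference in proportion of patients developing BK infection within 6 months will be determined using the chi-square test". The stratum does not appear. The only multivariable work in that section is "Univariate and multivariate proportional hazards Cox models will be developed to determine the risk factors of study outcomes". It names no covariates, is framed as a search for risk factors, and is not the treatment comparison on the primary endpoint.

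On size, section 4.1.2 states "A total of 180 kidney transplant recipients will be enrolled", and the synopsis gives the ratio as "2:1 study regimen to comparator group". No alpha, power, event rate or effect size goes with these figures.

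**The concern.** A factor is normally chosen for stratification because it is expected to affect the outcome. Section 1.1 gives a general reason to expect that here: "emergence of BK virus correlates with the more potent immunosuppressive agents currently used to lower acute rejection rates". If the expectation is right, a test that pools the strata counts the difference between strata as noise. With about 60 patients on placebo and no documented power margin, a few points of power are worth keeping if they cost little.

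The strength of the association is unknown. Section 1.1 speaks of immunosuppression in general, and nowhere is a BK rate given by induction. The question is therefore how much is lost if induction is a strong predictor, and what a stratified test would cost if it is not.

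**Working it through.** **Inputs from the documents.** N = 180 at 2:1, so 120 versus 60 if all are analysed; binary endpoint at 6 months; one binary stratum. The N of 180 cannot be reproduced, because none of its inputs is stated.

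**Assumed inputs.** Two-sided alpha 0.05, a common treatment odds ratio across strata, and a range of BK rates and alemtuzumab shares as listed below.

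**Why the tests differ.** The CMH statistic is [Σ(a_k − E_k)]² / ΣV_k, with E_k = n_1k·m_k/N_k and V_k = n_1k·n_0k·m_k·(N_k − m_k)/[N_k²(N_k − 1)]. Here a_k is the number of events on ciprofloxacin, m_k all events, and n_1k and n_0k the arm sizes in stratum k. If allocation is exactly 2:1 in each stratum, ΣE_k equals the expected count of the pooled chi-square, so the numerators coincide. Only the variances differ: the pooled one is p(1 − p) = Σw_k·p_k(1 − p_k) + Σw_k(p_k − p)², and CMH uses only the first, within-stratum term.

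Under the null the pooled Z then has standard deviation √(within/pooled), and the actual type I error is 2[1 − Φ(1.96/SD)]:

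- BK rate 50% with and 10% without alemtuzumab, 30% share: p = 0.22; pooled 0.1716; within 0.3×0.25 + 0.7×0.09 = 0.138; SD = √0.804 = 0.897; error 2.9%.
- 40%/10%, 50% share: p = 0.25; pooled 0.1875; within 0.165; SD = √0.88 = 0.938; error 3.7%.
- 20%/10%, 30% share: p = 0.13; pooled 0.1131; within 0.111; SD = 0.991; error 4.8%.

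**Simulation, first set.** 200,000 trials per cell (standard error about 0.1 point), no continuity correction, alemtuzumab share 20, 30 or 50%, treatment odds ratio 0.35 or 0.40. Entries are CMH power minus chi-square power, in points.

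| Placebo BK rate with/without alemtuzumab | Induction OR | Exact 2:1 within strata | Simple 2:1, stratum ignored |
|---|---|---|---|
| 10/10 | 1 | −1.1 to −0.6 | −0.4 to −0.3 |
| 15/15 | 1 | −1.9 to −1.2 | −0.4 to −0.3 |
| 20/20 | 1 | −0.9 to −0.6 | −0.5 to −0.4 |
| 25/15 | 1.9 | −1.0 to +0.2 | −0.2 to −0.1 |
| 20/10 | 2.3 | −1.0 to −0.5 | −0.1 to +0.1 |
| 30/15 | 2.4 | −0.4 to +1.3 | +0.1 to +0.5 |
| 30/10 | 3.9 | 0.0 to +1.5 | +0.8 to +1.3 |
| 40/10 | 6.0 | +1.5 to +3.5 | +2.1 to +3.1 |
| 50/10 | 9.0 | +4.1 to +6.6 | +4.0 to +5.6 |

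Examples at treatment OR 0.35 with balance, chi-square versus CMH: 50/10 at 30% share, 55.4% versus 61.3%; 40/10 at 50% share, 65.0% versus 68.1%; 20/10 at 30% share, 48.1% versus 47.6%; 15/15 at 20% share, 54.1% versus 52.3%.

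Chi-square type I error with balance was 4.3–4.5% at 30/10, 3.7% at 40/10, 3.0–3.1% at 50/10 and 4.7–5.3% elsewhere. This agrees with the hand calculation. Without balance it was 4.9–5.1%. CMH was 4.8–5.2% throughout.

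**Simulation, second set.** Overall rates of 20% versus 10%, 25% versus 10%, 30% versus 15% and 40% versus 20%; shares 20, 35 and 50%; balanced strata. With no induction effect, chi-square power is about 46%, 74%, 65% and 81% respectively. CMH minus chi-square, in points: induction OR 1, −0.6 to −0.1; OR 2, +0.1 to +0.8; OR 3, +0.9 to +1.7; OR 5, +2.2 to +3.7; OR 10, +3.5 to +9.7. At 25% versus 10% with a 35% share, power goes from 68.4% to 71.6% at OR 5 and from 61.8% to 68.5% at OR 10.

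**The case against.** The strongest reply is that nothing is broken. A chi-square named in advance is a standard and legitimate test, and any miscalibration is in the conservative direction. The harm depends on an association the documents never quantify, and in much of the first set CMH does nothing or does slightly worse. All of this stands. It limits the point to a refinement and places it below larger gaps, such as the absent justification for 180 subjects.

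A second reply is that simple 2:1 assignment is not the design described. Sections 4.1 and 5.2.4 say the trial is stratified, and assigning patients in order of qualification is compatible with a separate list per stratum. That is fair: the last column of the table is a sensitivity check. It shows that the gain with a strong predictor does not depend on how the schedule is built.

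A third reply is that the planned Cox models could include both treatment and induction. They could, but the plan does not say so, and they would not give a stratified test of the 6-month proportion.

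The two simulation sets also place the threshold for a useful gain differently. In the first, gains above 1.5 points appear only at an odds ratio of 6 or more. In the second, they begin at about 3. No single cut-off should be quoted, because it moves with the assumed rates.

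**Conclusion.** The point holds and is minor. The plan stratifies randomization and then leaves the stratum out of its primary test. This does not threaten validity. With balanced strata and a strong predictor the chi-square is conservative (down to about 2.3–3.1% at induction odds ratios of 9 to 10), while CMH stays near 5%. The power given up is roughly 1 to 4 points at odds ratios of about 3 to 6 and about 4 to 10 points at 9 to 10. At odds ratios of about 2 to 2.5 the difference is between −1.0 and +1.3 points. With no association CMH costs 0.1 to 1.9 points.

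These figures assume two-sided 0.05, all 180 analysed, a common treatment odds ratio, and rates and shares that the documents do not supply. Whether the trial would gain in practice depends on how strongly induction predicts BK infection at this center.

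**What to change.** In section 8.1.1, make the primary test a Cochran-Mantel-Haenszel test stratified by the alemtuzumab stratum used at randomization. Report the Mantel-Haenszel stratum-adjusted risk difference with its 95% CI. Keep the unstratified chi-square as a sensitivity analysis.

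This is a short edit to the analysis plan. It needs no new data, visits or subjects, because the stratum is fixed at enrollment (section 5.2.4). The price is the possible loss already quantified: at most about 2 points if induction turns out not to be prognostic, and at most about 1 point if it is a weak or moderate predictor. The choice should be made before unblinding so that it is clear which analysis is primary.

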##### **4.1.1 Study Endpoints**

###### **4.1.1.1 Primary Endpoint**

The primary endpoint will be the proportion of patients developing BK infection at 6 months post-transplant. BK infection is defined as the presence of a detectable BK viral load in plasma by polymerase chain reaction (PCR), or the presence of BK viral inclusions on kidney biopsy specimens. All detectable PCRs must be confirmed by repeat PCR to be considered positive.

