#### **6.4.2 Post-treatment Data Collection**

Patients will remain on study medication for 90 days post-transplant. All routine standard of care procedures/visits will apply. Patients are to have routine BK PCR drawn at 1, 2, 3, 6, 9, and 12 months post-transplant. Study visits will occur at baseline, 2 weeks, and 1, 2, 3, 6, 9, and 12 months post-transplant.

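### The primary chi-square needs a month-6 BK status for every dosed subject, but event-free subjects who leave early have none and no rule covers them

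*Combined protocol and SAP*

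**What the plan says.** Section 4.1.1.1 sets a binary endpoint: "The primary endpoint will be the proportion of patients developing BK infection at 6 months post-transplant". A detectable PCR needs confirmation: "All detectable PCRs must be confirmed by repeat PCR to be considered positive". Section 8.1.1 names the test: "The primary endpoint of the difference in proportion of patients developing BK infection within 6 months will be determined using the chi-square test". The analysis set is defined there too: "The ITT population will be defined as all randomized subjects who take at least one dose of the assigned therapy after randomization".

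On follow-up, section 6.4.2 says: "Patients are to have routine BK PCR drawn at 1, 2, 3, 6, 9, and 12 months post-transplant". Nothing is scheduled between months 3 and 6. Several sections let a subject leave before then:

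- Sections 5.1.4.1 and 5.1.4.2 allow the investigator to consider withdrawal from the study after 14 days off study drug.
- Section 9.2.1 sets follow-up after stopping study drug at 30 days from the last dose.
- Section 6.5.3 asks early leavers to attend a final safety visit. If they cannot, it seeks adverse events, rejection, graft loss and death, but does not list BK status. PCR monitoring afterwards is something standard of care may include, not a requirement.

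A method that handles censoring is named for a secondary endpoint only: "Time to BK infection and graft survival will be estimated using Kaplan-Meier methodology". No section says how the primary test treats a dosed subject with unknown month-6 status, or a death or graft loss before month 6.

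**The concern.** A subject with confirmed BK infection before leaving is a known event. A subject last seen PCR-negative, or with a detectable PCR not yet repeated, is neither a yes nor a no at month 6, yet the 2x2 table needs one or the other.

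One arm receives an antibiotic with its own adverse effects (section 10.4.1.1), and section 4.1.1.3 tracks discontinuation for related adverse events, so unequal exits are plausible. If the rule is left open, it can be chosen after the data are seen, and the primary p-value can depend on that choice.

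**Working it through.** **Inputs from the documents.** Total size: "A total of 180 kidney transplant recipients will be enrolled". Allocation: "1:2 ratio standard of care (placebo), or 90 days of once-daily ciprofloxacin". Together these give 60 placebo and 120 ciprofloxacin. PCRs up to the endpoint fall at months 1, 2, 3 and 6. The 180 cannot be reproduced, because the plan gives no alpha, power, event rates or dropout allowance.

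**Assumptions.** Two-sided 0.05. True 6-month incidence p of 20% in both arms (null case) or 20% against 10%. Constant infection hazard, so F(t) = 1 - (1 - p)^(t/6). A fraction q leaves, uniformly over months 0 to 6 and independently of BK.

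**Step 1: infections detected among leavers.** A leaver's infection counts only if it was present at the last PCR before exit:

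D = F(1)/6 + F(2)/6 + 3F(3)/6

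For p = 20%: F(1) = 0.0365, F(2) = 0.0717, F(3) = 0.1056, so D = 0.0708. For p = 10%: D = 0.0343.

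**Step 2: two scoring rules.**

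- Event-free leavers scored BK-free: A = p - q(p - D)
- Event-free leavers dropped, infected leavers kept: B = A / [1 - q(1 - D)]

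| True 20% in both arms | Placebo | Ciprofloxacin | Difference |
|---|---|---|---|
| A, exits 5% and 15% | 0.1935 | 0.1806 | -1.3 points |
| B, same exits | 0.1935/0.9535 = 0.2030 | 0.1806/0.8606 = 0.2099 | +0.7 |
| A, exits 10% and 30% | 0.1871 | 0.1612 | -2.6 |
| B, same exits | 0.1871/0.9071 = 0.2062 | 0.1612/0.7212 = 0.2236 | +1.7 |

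Under rule A the type I error is about 5.7% in the milder case and about 7.6% in the stronger one.

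**Step 3: a real effect.** With 20% against 10% and equal 10% loss, rule A gives 0.1871 and 0.0934, a difference of -9.4 instead of -10.0 points. With exits of 5% and 15%, the chance of significance is about 51% under A and 41% under B. At 10% and 30% it is 56% and 34%.

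**Step 4: censoring.** A life table at the PCR visits multiplies (1 - events/at risk) over visits. With independent exits, the fraction still under follow-up multiplies both events and at risk, and cancels. Each arm therefore returns 1 - 0.80 = 20%, a difference of zero. Simulation agrees (+0.0002 at exits of 5% and 15%).

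**Step 5: competing events.** If every exit is a competing event and nothing is censored, cumulative incidence equals detected infections divided by all dosed subjects, which is rule A. In one simulated arm (20% incidence, 30% exits) both were 16.02%, while one minus Kaplan-Meier was 19.8%.

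**Step 6: one illustrative trial.** Take 12/60 and 12/120 detected events, with 3 and 18 event-free subjects lost (5% and 15%):

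| Rule | Placebo | Ciprofloxacin | Difference | p (uncorrected chi-square) |
|---|---|---|---|---|
| Lost = BK-free | 12/60 | 12/120 | -10.0 points | 0.063 |
| Lost dropped | 12/57 | 12/102 | -9.3 | 0.117 |
| All lost = infected | 15/60 | 30/120 | 0.0 | 1.0 |
| Only lost placebo = infected | 15/60 | 12/120 | -15.0 | 0.008 |
| Only lost ciprofloxacin = infected | 12/60 | 30/120 | +5.0 | 0.45 |

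**The case against.** A reader might infer that the plan scores early leavers BK-free. It does not say so. It is silent, and scoring them as infected, imputing, or dropping every leaver is equally open. Dropping every leaver, infected or not, is unbiased if loss is unrelated to BK, even with unequal rates. Dropping anyone also departs from the stated analysis set.

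A reader might also expect cumulative incidence with competing events to remove the bias for deaths and graft losses. Step 5 shows it does not: for those events it reproduces the crude proportion. The near-zero bias in Step 4 belongs to censoring. Nor do the documents say that plasma PCR stops at graft loss.

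Stopping an antibiotic is not leaving the study, and treatment ends at 90 days while the exits above run to month 6. This is fair as to how many will leave. The timing does not rescue the crude proportion: with exits uniform over months 0 to 3, D = [F(1) + F(2)]/3 = 0.0361, and rule A at 5% and 15% gives -(0.15 - 0.05)(0.20 - 0.0361) = -1.6 points.

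Better collection is also a direct remedy for withdrawals, since PCR after stopping is only optional under section 6.5.3. Finally, the Kaplan-Meier curve for time to BK infection will be reported anyway. That helps the reader, but leaves the primary test without a rule.

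**Conclusion.** The point holds as a gap in the primary analysis: unknown status is foreseeable, no rule covers it, and two natural rules give different answers. The bias is modest, about 1 to 3 points at the assumed exit rates, and would be larger only if loss were related to BK or exits more unequal. Equal losses create no false difference, but they do shrink a real one under BK-free scoring. Exit rates, incidence and independence of loss from BK are all assumptions.

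The documents do not support saying that leavers will be scored BK-free, or that a competing-event analysis corrects for death and graft loss. The gain from changing the estimate comes from withdrawals and other losses. Censoring does not correct withdrawal that is related to BK.

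**What to change.** In section 8.1.1, make the primary estimate the ciprofloxacin-minus-placebo difference in cumulative incidence of BK infection at month 6, with its 95% confidence interval and test, and specify:

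- Withdrawals and other losses are censored at the last PCR, on the stated assumption that leaving is unrelated to BK.
- Death is a competing event. Graft loss is one only if PCR follow-up ends there, and the plan should say whether it does.
- For competing events the estimate equals the crude proportion and targets infection that actually occurs.
- The chi-square with unknown counted as BK-free, and with unknown counted as infected, is reported as sensitivity analyses. A last detectable but unrepeated PCR is classed as unknown.

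The cost is SAP wording and a few lines of code on data already collected. The primary result becomes slightly harder to explain than a 2x2 table.

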###### **4.1.1.3 Additional Evaluations to be Tracked**

The following safety parameters will be assessed and measured during the study period:

- Dose discontinuation due to adverse event related to therapy
- Serum creatinine concentrations at 1, 3, 6, 9, and 12 months post-transplant
- Graft loss at 1 year
- Death at 1 year

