### 6.5.2 Screening and Eligibility

Between day -14 and day 7 post-transplant after obtaining informed consent, subjects who fulfill all of the inclusion criteria and none of the exclusion criteria will be enrolled into the study. Documentation of the fulfillment of criteria will be included in the study files.

 Medical history includes history of age, diagnosis for renal failure, history of diabetes, duration and type of dialysis, cytomegalovirus (CMV) serology, and HLA typing.

 Immunosuppressant medications, including medications used to treat rejection, and concomitant anti-microbial use will be captured. At months 6,9 and 12 only immunosuppressant dosages are required.

. Transplant information includes donor demographics (age, sex, race) and CMV serology, donor history (terminal serum creatinine, cause of death), type of transplant (ECD, DCD, or SCD), ischemia times, peak PRA and most recent PRA prior to transplant.

 Subject must meet all Inclusion and Exclusion Criteria prior to randomization.

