### 16.2 Appendix 2: Equation for Estimating Glomerular Filtration Rate

IDMS-traceable MDRD equation for estimating Glomerular Filtration Rate (eGFR).

$GFR \text{ (mL/min/1.73 m}^2\text{)} = 175 \times (S_{cr})^{-1.154} \times (\text{Age})^{-0.203} \times (0.742 \text{ if female}) \times (1.212 \text{ if African American})$  (conventional units)

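### Serum creatinine at five visits goes to unadjusted t-tests or ANOVA with no rule for the repeated values; an adjusted repeated-measures model would be more precise at almost no cost

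*Combined protocol and SAP*

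**What the plan says.** Section 4.1.1.3 lists "Serum creatinine concentrations at 1, 3, 6, 9, and 12 months post-transplant" under the sentence "The following safety parameters will be assessed and measured during the study period". Creatinine is on neither the primary nor the secondary endpoint list.

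Section 8.1.1 covers it with a general rule: "All secondary and safety outcomes will be analyzed using chi-square or fisher exact testing for categorical variables". For a continuous outcome such as creatinine, the same sentence prescribes "analysis of variance or t-tests for continuous variables". The section gives no visit of interest, summary measure, repeated-measures method, covariate, significance level or multiplicity rule for this outcome. The only multivariable method it names is "Univariate and multivariate proportional hazards Cox models will be developed to determine the risk factors of study outcomes", which does not apply to a creatinine value.

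Appendix 2 gives the MDRD equation, which needs creatinine, age, sex and race. It is the only eGFR equation in the document, and the only stated use of eGFR is the threshold of 30 in section 5.1.3.1. On recipient data, footnote 1 (section 6.5.2) reads "Medical history includes history of age, diagnosis for renal failure, history of diabetes, duration and type of dialysis" and goes on to CMV serology and HLA typing. It has recipient age but not recipient sex or race. Footnote 3 lists sex and race for the donor only.

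**The concern.** Creatinine is the only continuous measure of graft function among the endpoints and tracked evaluations of section 4.1.1, and each subject contributes up to five correlated values. A bare instruction to use t-tests or ANOVA leaves three gaps.

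- The analyst can choose after seeing the data whether to report one visit, five visits or some average.
- A test at a single visit ignores what the same subject's other visits say. Later visits may well be missing: section 9.2.1 asks for 30 days of follow-up after the last dose. For withdrawn subjects who miss the final visit, the fallback in section 6.5.3 seeks adverse events, rejection, graft loss and death, but not creatinine.
- Part of the spread in raw creatinine reflects sex, race and age and says nothing about kidney function. With about 60 placebo subjects, that avoidable noise matters.

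**Working it through.** **Inputs from the documents.** "A total of 180 kidney transplant recipients will be enrolled" (section 4.1.2), allocated 2:1, so 180 × 2/3 = 120 ciprofloxacin and 60 placebo. There are five creatinine visits. Appendix 2: GFR = 175 × Scr^-1.154 × age^-0.203 × 0.742 if female × 1.212 if African American. The 180 comes with no significance level, power or effect size, so there is no stated figure to reproduce, and this point does not depend on one.

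**Assumptions (not in the documents).** Two-sided 5% per test; between-visit correlation 0.7 to 0.9; 40% women; 30% African American; age mean 52, SD 13; total SD of log creatinine 0.30 to 0.45; true GFR unrelated to sex and race; the Appendix 2 factors apply to these recipients.

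**Step 1: creatinine at equal GFR.** Solving the equation for creatinine:

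- women against men: 0.742^(1/1.154) = 0.772, or 23% lower;
- African American against other recipients: 1.212^(1/1.154) = 1.181, or 18% higher;
- age 65 against 35: (65/35)^(-0.203/1.154) = 0.897, or 10% lower.

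**Step 2: share of variance due to sex and race.** On the log scale the shifts are ln(0.742)/1.154 = -0.2586 and ln(1.212)/1.154 = 0.1666. Variance explained = 0.4 × 0.6 × 0.2586² + 0.3 × 0.7 × 0.1666² = 0.0160 + 0.0058 = 0.0219.

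| SD of log creatinine | Share explained |
|---|---|
| 0.30 | 0.0219/0.0900 = 24% |
| 0.35 | 0.0219/0.1225 = 18% |
| 0.45 | 0.0219/0.2025 = 11% |

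**Step 3: effect on the arm comparison.** Trials of 120:60 were simulated at one visit, with SD of log GFR 0.3, 0.4 or 0.5. That gives a total SD of log creatinine of about √((0.3/1.154)² + 0.0219) = 0.30 up to √((0.5/1.154)² + 0.0219) = 0.46, close to the range above. The power columns use an illustrative effect of 0.15 on log GFR.

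| SD log GFR | Variance cut by adjusting for age, sex, race | Power, raw t-test | Power, log t-test | Power, log adjusted |
|---|---|---|---|---|
| 0.3 | 25% | 0.74 | 0.77 | 0.88 |
| 0.4 | 15% | 0.53 | 0.58 | 0.66 |
| 0.5 | 10% | 0.37 | 0.42 | 0.47 |

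With no true effect, the raw t-test rejected in 4.8% to 5.1% of trials. Omitting the covariates therefore costs precision and does not add false positives.

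**Step 4: five tests, if any one significant visit counts.** Independent tests would give 1 - 0.95^5 = 22.6%, but visits on the same subject are correlated. From 200,000 draws per setting:

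| Correlation | Equal between all visits | Decaying, per 3 months |
|---|---|---|
| 0.7 | 14.7% | 16.7% |
| 0.8 | 12.7% | 14.4% |
| 0.9 | 10.2% | 11.5% |

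**Step 5: gain from pooling visits.** The SE of a five-visit average relative to one visit is √((1 + 4ρ)/5): 0.87 at ρ = 0.7 and 0.96 at ρ = 0.9.

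**Step 6: why sex and race belong on the list.** At age 50 and creatinine 2.0 mg/dL, Appendix 2 gives an eGFR of 35.5 (man), 43.1 (African American man), 26.4 (woman) and 32.0 (African American woman). These fall on both sides of the section 5.1.3.1 threshold of 30, so eGFR by this equation cannot be checked from study data without both fields.

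**The case against.** The strongest reply is that nothing here is an error. An unadjusted comparison in a randomised trial is valid. Creatinine is a tracked safety parameter, and strict multiplicity control is often left out of safety monitoring because it makes harm harder to see. Appendix 2 serves a dosing threshold, and eGFR is not an outcome, so the plan does not contradict itself by leaving the equation out of the comparison. Graft loss is tracked separately, and graft survival has its own Kaplan-Meier analysis. All of this stands, and it limits the weight of the point.

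It also rules out four stronger readings that a reader might infer:

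- *That the plan commits to five separate tests.* This is a natural reading, but section 8.1.1 does not say so, and analysis of variance can take a repeated-measures form. The documents show only that the handling is unspecified.
- *That false positives are inflated as such.* The 10% to 15% needs a rule that any one significant visit is a finding. The plan states neither such a rule nor a significance level.
- *That ignoring sex, race and age biases the comparison.* Randomisation balances them on average, and the test keeps its size.
- *That recipient sex and race will not be collected.* Footnote 1 is worded as open-ended and the eCRF is not itemised, so both may well be recorded. They are simply not named.

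A further fair objection concerns the remedy. The average over months 1 to 12 mixes visits within or at the end of the 90-day course (months 1 and 3) with off-drug visits (6, 9 and 12). It could dilute a transient on-drug effect or a late one, and by Step 5 it gains only 4% to 13% in SE. It should not be the sole comparison. None of this answers the loss of precision or the silence on repeated values.

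**Conclusion.** The point holds as a modest improvement. Section 8.1.1 assigns a five-visit outcome to t-tests or ANOVA with no covariates and no statement of how the repeated values are used. The comparison is unbiased but less precise than it could be: roughly 10% to 25% of the variance of the arm difference is avoidable under the assumed case mix and spread. The equal-GFR ratios of 0.772 and 1.181 follow directly from Appendix 2, whereas the variance figures rest on the assumptions listed. The false-positive figure of about 10% to 15% is conditional on how the results are read and on an assumed correlation of 0.9 to 0.7; decaying correlation gives slightly more. The primary endpoint and the sample size are not touched.

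**What to change.** In section 8.1.1, replace the general rule for creatinine with one mixed model for repeated measures on log creatinine at months 1, 3, 6, 9 and 12. Include arm, visit, arm-by-visit, the alemtuzumab stratum used at randomisation, and recipient age, sex and race. Appendix 2 eGFR could be the outcome instead; on the log scale with log age, sex and race in the model, the arm difference changes only by the factor -1.154.

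Report the arm difference with its 95% CI at each visit. Name in advance the visit or contrast that is the main comparison, choosing deliberately between on-drug and off-drug visits and not relying only on the month 1 to 12 average. State the significance level. Report graft loss and death by arm beside the model.

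In footnote 1 of section 6.5.2, name recipient sex and race.

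The cost is some SAP wording, slightly more analysis work and two demographic fields. Section 6.5.1 already schedules creatinine at all five visits, so no procedure is added. One limit remains: a mixed model in effect extrapolates creatinine past graft loss or death, so its estimates must be read together with those events.
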